## 1.2 Investigational Product

Pimavanserin is an atypical antipsychotic that is present in the investigational product as pimavanserin tartrate salt with the chemical name, urea, *N*-[(4-fluorophenyl)methyl]-*N*-(1-methyl-4-piperidinyl)-*N*'-[4-(2-methylpropoxy)phenyl]methyl]-, (2*R*,3*R*)-2,3-dihydroxybutanedioate (2:1). In April 2016, pimavanserin was approved in the United States (US) for the treatment of hallucinations and delusions associated with Parkinson's disease psychosis (PDP).

Pimavanserin is a novel small molecule designed to specifically block serotonergic neurotransmission mediated by the 5-hydroxytryptamine (5-HT [serotonin]) 2A (5-HT2A) receptor. At higher doses, pimavanserin may block 5HT2C receptors (Vanover et al. 2006). Pimavanserin shows no appreciable activity at dopaminergic, adrenergic, histaminergic, or muscarinic receptors. Activity at these receptors has been implicated in a range of dose-limiting side effects associated with existing antipsychotic drugs including cognitive dulling (Saeedi et al. 2006; Mehta et al. 2004; Peretti et al. 1997) and an increased risk of mortality in elderly patients with dementia (Wang et al. 2005). On the basis of its novel receptor binding profile, pimavanserin may be effective in treating behavioral problems and mood disorders, and have added benefits with regard to overall tolerability relative to other antipsychotic agents.

In this study, subjects will be asked to take pimavanserin tablets once daily as an oral formulation.

## 1.3 Previous Clinical Experience

Pimavanserin is an atypical antipsychotic that is approved for the treatment of hallucinations and delusions associated with PDP. Studies have also been conducted in Alzheimer's disease

psychosis (ADP) and schizophrenia and studies are ongoing in schizophrenia, Alzheimer's disease agitation and aggression, and major depressive disorder. The clinical program for PDP and the Phase 2 ADP study are reviewed below as the study population (elderly subjects) is most closely aligned with the intended study population of this protocol. A more complete discussion of these studies, as well as other completed and ongoing pimavanserin clinical studies, is available in the pimavanserin Investigator's Brochure (IB).

### 1.3.1 Parkinson's Disease Psychosis Program

The scope of the development program for pimavanserin is the largest ever conducted in PDP. At the time of approval, 616 mostly older, late-stage PDP subjects had been evaluated in 16 countries over a span of >10 years. Clinically meaningful efficacy was established in Study ACP-103-020, a 6-week, placebo-controlled Phase 3 study. This efficacy was supported by data from additional short-term Phase 2b/3 studies. In ACP-103-020, pimavanserin 34 mg consistently demonstrated statistically significant efficacy across multiple and independent endpoints, subject subgroups, and sensitivity analyses. Improvements in sleep and daytime wakefulness were also observed. These clinical benefits were achieved without worsening of PD motor symptoms and without a number of other safety concerns associated with atypical antipsychotics.

Pimavanserin is considered to be generally safe and well tolerated. Across all clinical studies of pimavanserin, the most frequently reported treatment-emergent adverse events (TEAEs) were in the central nervous system (CNS), gastrointestinal, and psychiatric systems. Most events were mild to moderate in intensity. The most common CNS TEAEs included dizziness (including postural), headache, and somnolence (drowsiness). Common gastrointestinal disturbances included dyspepsia, nausea, constipation, and vomiting. Severe nausea and vomiting were dose limiting in a few cases. Reported psychiatric conditions included agitation, insomnia, and confusional state. Refer to the current IB for the most up-to-date Reference Safety Information for pimavanserin.

Clinical and nonclinical safety pharmacology studies of pimavanserin suggest that it is a selective 5-HT2A antagonist. The safety profile of pimavanserin has been assessed in a thorough QT study with doses of pimavanserin ranging from 17 to 68 mg. In the Phase 3 PDP program, an average prolongation of approximately 5 to 8 ms was observed with pimavanserin 34 mg.

The US package insert for pimavanserin has a boxed warning that elderly patients with dementia-related psychosis treated with antipsychotic drugs are at an increased risk of death. Pimavanserin is not approved in the treatment of patients with dementia-related psychosis unrelated to the hallucinations and delusions associated with PDP.

Additional information is provided in the pimavanserin IB and in the NUPLAZID® (pimavanserin) US package insert.

### 1.3.2 Alzheimer's Disease Psychosis

Evidence from the recently completed Phase 2 study (ACP-103-019) suggests that pimavanserin is effective in reducing hallucinations and delusions in subjects with ADP.

Study ACP-103-019 was a Phase 2, 12-week randomized, double-blind, placebo-controlled, single-center study to assess the safety and efficacy of pimavanserin 34 mg once daily in nursing home subjects with ADP. Eligible subjects were required to have a score of 4 or greater on either the hallucinations or delusions scale of the Neuropsychiatric Inventory-Nursing Home Version (NPI-NH) or a combined hallucinations and delusions score of 6 or greater. The primary efficacy endpoint was change from Baseline to Day 43 in the NPI-NH psychosis score (delusions+hallucinations domains).

A total of 181 subjects were randomized (n=90 pimavanserin 34 mg and n=91 placebo) with 178 subjects included in the Full Analysis Set (FAS) (n=87 pimavanserin and n=91 placebo). The mean (standard error [SE]) age of subjects was 85.9 (0.48) years. The mean (SE) Baseline NPI-NH psychosis score for all FAS subjects was 9.8 (0.39) with comparable mean scores in the pimavanserin (9.5) and placebo (10.0) groups. The mean (SE) Mini-mental State Examination (MMSE) score for all FAS subjects was 10.1 (0.40).

Efficacy results for the primary endpoint (NPI-NH psychosis score after 6 weeks of treatment [Day 43] demonstrated a significant ( $p=0.0451$ ; effect size [Cohen's  $d$ ]= -0.320) treatment effect for pimavanserin compared with placebo. Prespecified subgroup analyses supported a clinically relevant treatment effect in the pimavanserin group, as a larger effect size was generally observed in subjects with more severe psychosis. Similarly, the proportion of responders (subjects with 30% and 50% reductions from Baseline) was statistically significantly greater in the pimavanserin group compared to placebo (Table 1-1 [REDACTED]). [REDACTED] pimavanserin achieved improvement to Week 12 but the difference from placebo was not maintained [REDACTED] p between Weeks 6 and 12.

**Table 1-1 NPI-NH Psychosis Score Percent Responder Analysis – Full Analysis Set – Week 6 (Day 43)**

Treatment Group (% Responder)	Percent Improvement from Baseline				
	≥20%	≥30%	≥50%	≥75%	100%
Pimavanserin 34 mg	58.6%	55.2%	50.6%	27.6%	12.6%
Placebo	46.2%	37.4%	34.1%	16.5%	9.9%
p-value for test of group difference	0.0937	0.0159	0.0240	0.0656	0.5514

Source: ACP-103-019 Clinical Study Report

Note: Missing values were imputed as nonresponders.

With respect to safety, pimavanserin appeared to be well-tolerated with no new safety observations in this elderly and frail patient population compared to the pimavanserin PDP safety database. An equal number of post-randomization deaths were reported: 4 deaths in the pimavanserin group and 4 in the placebo group.

There were more serious adverse events (SAEs) reported in pimavanserin group (16.7%) than in the placebo group (11.0%). A review of the reported SAEs, both in the placebo and pimavanserin groups, did not reveal the presence of any common, underlying pathophysiologic mechanism or cause. However, there were fewer discontinuations due to treatment emergent adverse events (TEAEs) in the pimavanserin group (8.9%) compared with the placebo group (12.1%).

The most common TEAEs in the pimavanserin group were fall (23.3%), urinary tract infection (22.2%), and agitation (21.1%), which have been described as associated with this elderly frail patient population. Of these, agitation was reported more often in the pimavanserin group than in the placebo group.

The mean change from Baseline in the QTc interval in subjects treated with pimavanserin was 9.4 ms at 12 weeks (Day 85) with no significant outliers reported at Day 85 (>500 ms or delta ≥60 ms). One subject in the pimavanserin group and one subject in the placebo group had a delta ≥60 ms at Day 15. Each subject continued in the study.

Weight data were available for about half of the study participants at Day 85. Mean body weight and body mass index (BMI) remained relatively unchanged from Baseline to Day 85 in both treatment groups. Overall, 1 (1.8%) subject in the placebo group and 7 (14.6%) subjects in the pimavanserin group experienced weight decrease of ≥7% and 5 (8.8%) subjects in the placebo group and 4 (8.3%) subjects in the pimavanserin group experienced weight increase of ≥7%.

Changes from Baseline in MMSE were similar in placebo and pimavanserin group indicating that pimavanserin did not affect cognitive function in these patients. Similarly, treatment with

pimavanserin had no negative effect on motor function as measured by the Unified Parkinson's Disease Rating Scale (UPDRS) Part III scores.

### 1.4 Study Rationale

The rationale for the use of pimavanserin as monotherapy or adjunctive treatment for DPD is based on the following:

5-HT2A serotonin receptors represent important targets for depression. A variety of studies have shown antidepressant activity from compounds with potent antagonist or inverse agonist activity at 5-HT2A receptors, and to varying degrees 5-HT2C receptors, but low affinity to serotonin, norepinephrine, and dopamine transporters, either alone or when co-administered with selective serotonin reuptake inhibitors (SSRIs; see Table 1-2). These compounds include volinanserin, pruvanserin, ketanserin, ritanserin, mirtazapine, mianserin, and trazodone (see Table 1-2). Pimavanserin, with its potent activity as a 5-HT2A antagonist/inverse agonist and lesser activity as a 5-HT2C antagonist/inverse agonist, has a similar receptor profile to many compounds with antidepressant activity. Therefore, although there are no preclinical data on pimavanserin in animal models of depression, it would also be expected to have antidepressant activity.

**Table 1-2 Receptor Profiles of Pimavanserin and Compounds With Antidepressant Activity**

Target	PIM	RIT	VOL	PRUV	PIP	KET	MIRT	MIAN	TRAZ
SERT		Low	Low	Low	na	Low	Low	Low	350
NET		Low	Low	Low	na	Low	Low	70	Low
DAT		Low	Low	Low	na	Low	Low	Low	Low
5-HT 2A		0.1	0.2	0.7	5	2	70	3	35
5-HT 2C		3	125	Low	120	125	40	3	200
Other noteworthy targets		None	None	None	D4 (5) α2 (35)	α1 (15-20)	α2 (15-20) H1 (1)	α2 (4-20) H1 (1)	5-HT 1A (100)

Source: Data on file except for: pipamperone (Schotte et al. 1996); trazodone and mianserin (PDSP Ki database, see Roth et al. 2000); mirtazepine (Brayfield 2014); and (Wikström et al. 2002).

Abbreviations: α1=alpha1 adrenergic receptor; α2=alpha2 adrenergic receptor; DAT=dopamine transporter; H1=histamine 1 receptor; KET=ketanserin; MIAN=mianserin; MIRT=mirtazepine; NET=norepinephrine transporter; PIM=pimavanserin; PIP=pipamperone; PRUV=pruvanserin; RIT=ritanserin; SERT=serotonin transporter; TRAZ=trazodone; VOL=volinanserin.

Values represent the affinity (Ki) in nM of the indicated ligands and transporters/receptors. For "Other Noteworthy Targets", Ki values are provided in parentheses. "na" denotes not available. Low denotes Ki >1000 nM.

## 2 STUDY OBJECTIVES AND ENDPOINTS

### 2.1 Primary Objective

To assess the efficacy of pimavanserin for the treatment of depression in adults with Parkinson's disease

#### 2.1.1 Primary Endpoint

Change from Baseline to Week 8 in the Hamilton Depression Scale–17 items (HAMD-17) total score

### 2.2 Secondary Objectives

To explore the efficacy of pimavanserin in the following domains:

- Clinician's global assessment of treatment benefits
- Night time sleep and day time sleepiness
- Quality of life

#### 2.2.1 Secondary Endpoints

- Clinical Global Impression-Improvement (CGI-I)
- Change from Baseline in CGI-Severity (CGI-S)
- Change from Baseline in Scale of Outcomes in PD-Sleep Scale (SCOPA) night time sleep score
- Change from Baseline in SCOPA day time sleepiness score
- Proportion of responders (defined as  $\geq 50\%$  reduction from Baseline in HAMD-17 total score)
- Change from Baseline in EuroQol-5 dimensions-5 levels (EQ-5D-5L [REDACTED])

#### 2.3 Safety Objective

[REDACTED] depression in adults with Parkinson's disease

#### 2.3.1 Safety Endpoints

The safety endpoints for this study are as follows:

- Adverse events
- Vital signs
- 12-lead electrocardiogram (ECG)

- Hematology, serum chemistry, urinalysis
- Columbia Suicide Severity Rating Scale (C-SSRS)
- Mini-Mental State Examination (MMSE)
- Unified Parkinson's Disease Rating Scale (UPDRS) Part III

### **3 STUDY DESCRIPTION**

#### **3.1 Overview of Study Design**

This will be a multi-center, open-label study to assess the efficacy and safety of treatment with 34 mg pimavanserin in subjects with PD and depression. Approximately 20 sites will participate in this study. Each subject will participate in a screening and treatment period with regularly scheduled assessments (see [Figure S-1](#) and [Table S-1](#)).

#### **3.2 Screening Period (1-21 Days)**

Subjects will be assessed for eligibility and prohibited medications will be discontinued. Screening will be up to 3 weeks.

Investigators should not discontinue a subject's prohibited medication for the purpose of enrolling them into the study. Medications should be discontinued only if it is deemed clinically appropriate to do so. Subjects who are currently taking an SSRI/SNRI and a second antidepressant or antidepressant augmentation agent at a sub-therapeutic dose or for an inadequate duration at Screening can discontinue the second antidepressant or antidepressant augmentation agent before the Baseline visit if, in the opinion of the Investigator, the current treatment has been inadequate. Current or previous treatment with an antidepressant is not required. The Medical Monitor may also be consulted.

#### **3.3 Treatment Period (8 Weeks)**

After all screening assessments are completed, eligible subjects will return to the clinic for the Baseline evaluation. After Baseline assessments are completed, subjects will be enrolled and will begin receiving pimavanserin 34 mg once daily (OD). Study medication will be provided to the subjects to take home with instructions to take the medication approximately the same time each day. Drug should be dispensed at Baseline and Week 4, with returned used container(s) at Week 4 and all containers and unused drugs returned at Week 8.

At approximately 2, 4, and 6 weeks after start of dosing of study drug, subjects will return to the clinic for assessments. Safety measures, HAMD-17, C-SSRS, CGI-S, and CGI-I will be evaluated at all visits. Subjects will complete the SCOPA, EQ-5D-5L, MMSE, and UPDRS Part III at Baseline and Week 4.

At the end of the 8 weeks of study drug treatment, subjects will return to the clinic for their final clinical evaluation. All assessments will be completed and unused study drug and containers will be collected.

### **3.4 Safety Follow-up Period (Approximately 2 Weeks)**

Approximately 2 weeks after the last dose of study drug, subjects will have a safety follow up telephone call visit.

## **4 SUBJECT ELIGIBILITY AND WITHDRAWAL CRITERIA**

### **4.1 Subject Selection and Withdrawal**

To be eligible for this study, subjects must meet all of the inclusion criteria and none of the exclusion criteria.

Protocol waivers for eligibility will not be granted by the Sponsor under any circumstances. If, during the course of the study, it is discovered that the subject did not meet all eligibility criteria, she or he will be discontinued, unless the discontinuation presents an unacceptable medical risk. The justification to allow the subject to continue in the study will be made by the Sponsor, with medical input from the Investigator, and will be documented. If allowed to remain in the trial, this will be reported as a major protocol deviation and not a waiver.

Subjects who screen fail will be allowed to re-screen with the permission of the Medical Monitor, provided the screen failure was due to a temporary condition that subsequently resolved.

### **4.2 Inclusion Criteria**

1. Is a male or female  $\geq 50$  years of age
2. Can understand and provide signed informed consent, request for medical records and/or subject privacy form if applicable according to local regulations [REDACTED]  
[REDACTED] can be reliably rated on assessment scales (in the opinion of the Investigator), and has a reliable [REDACTED] (personal friend, or professional caregiver) who can report on the subject's health-related quality of life
4. Has a clinical diagnosis of idiopathic Parkinson's disease with a minimum duration of 1 year, defined as the presence of at least three of the following cardinal features, in the absence of alternative explanations or atypical features:
  - a. rest tremor
  - b. rigidity
  - c. bradykinesia and/or akinesia

- d. postural and gait abnormalities
- 5. Meets clinical criteria for depression with Parkinson's disease as listed in the NINDS/NIMH Guidelines ([Marsh et al. 2006](#))
- 6. Has a Hamilton Depression Scale-17 item (HAM-D-17) total score  $\geq 15$  at Screening and Baseline
- 7. If currently taking an antidepressant, is being treated with only one of the following SSRI or SNRI antidepressants at a dose within the United States Food and Drug Administration (US FDA)-approved dose range. Subjects who are currently taking a second antidepressant or antidepressant augmentation agent at a sub-therapeutic dose or for an inadequate duration at Screening, and can be discontinued from this agent before the Baseline visit (in the opinion of the Investigator), may be eligible for the study.
  - a. Citalopram
  - b. Escitalopram
  - c. Paroxetine
  - d. Fluoxetine
  - e. Sertraline
  - f. Vortioxetine
  - g. Duloxetine
  - h. Venlafaxine
  - i. Desvenlafaxine
  - j. Venlafaxine XR
  - k. Vilazodone
  - l. Levomilnacipran

Current or previous treatment with an antidepressant is not required [REDACTED]  
[REDACTED] appropriate (e.g.,  
symptoms are not well controlled or the subject cannot tolerate the [REDACTED]  
[REDACTED]

- 8. If the subject is currently taking an antidepressant and has an improvement in depression of less than 75% when working at its best, as confirmed by the Massachusetts General Hospital Antidepressant Treatment Questionnaire (MGH ATRQ)
- 9. Has a Mini Mental State Exam (MMSE) score  $\geq 21$
- 10. Is on a stable dose of anti-Parkinson's medication for at least 1 month prior to Screening

11. If the subject is female, she must be of non-childbearing potential (defined as either surgically sterilized [history of a bilateral oophorectomy, bilateral tubal ligation, or a partial or complete hysterectomy] or at least 1 year postmenopausal) OR must agree to use TWO clinically acceptable methods of contraception, if sexually active, throughout the study and for at least 1 month prior to the Baseline visit (Visit 2) and 41 days following completion of the study. Clinically acceptable methods of contraception include oral, injectable, transdermal, or implantable contraception, an intrauterine device (IUD), and a condom, diaphragm, cervical cap, or sponge with spermicide. Only one of the two clinically acceptable methods can be a hormonal method.
12. If the subject is a female of childbearing potential, she must have a negative serum pregnancy test at Screening and a negative urine pregnancy test at Baseline

#### 4.3 Exclusion Criteria

1. Use of an antipsychotic within 3 weeks or 5 half-lives of Baseline (whichever is longer)
2. Has greater than New York Heart Association (NYHA) Class 2 congestive heart failure or Class 2 angina pectoris, sustained ventricular tachycardia, ventricular fibrillation, or torsade de pointes, or syncope due to an arrhythmia
3. Had a myocardial infarction within the 6 months prior to Screening
4. Has a known personal or family history or symptoms of long QT syndrome
5. Has any of the following ECG results at Screening (the ECG may be repeated once at Screening in consultation with the Medical Monitor):
  - a. If the subject is not on citalopram, escitalopram, or venlafaxine
    - i. QTcF >450 ms, if QRS duration <120 ms
    - ii. QTcF >470 ms, if QRS duration ≥120 ms
  - b. If the subject is on citalopram, escitalopram, or venlafaxine
    - i. QTcF >450 ms, if QRS duration <120 ms
    - ii. QTcF >450 ms, if QRS duration ≥120 ms
6. Has clinically significant laboratory abnormalities that, in the judgment of the Investigator or Medical Monitor, would jeopardize the safe participation of the subject in the study
7. Evidence of severe or medically significant hepatic or renal impairment on laboratory tests as assessed by the Investigator or Medical Monitor
8. Has uncontrolled diabetes or a glycosylated hemoglobin (HbA1c) >8% at Screening

9. Has laboratory evidence of hypothyroidism at Screening, as measured by thyroid-stimulating hormone (TSH) and reflex free thyroxine (T4). If TSH is abnormal and the reflex free T4 is normal, the subject may be enrolled
10. Has a body mass index (BMI) of <19 or >35
11. Has a known history of a positive hepatitis B virus (HBV), hepatitis C virus (HCV), or human immunodeficiency virus (HIV) test
12. Has a history of PD psychosis, schizophrenia, or other psychotic disorder, or bipolar I or II disorder. Subjects who are currently being treated for eating disorder, obsessive-compulsive disorder (OCD), attention deficit hyperactivity disorder (ADHD), panic disorder, acute stress disorder, or posttraumatic stress disorder (PTSD), according to DSM-5 criteria, are also not eligible.
13. Has a current diagnosis of delirium
14. Has a current primary diagnosis of borderline, antisocial, paranoid, schizoid, schizotypal, or histrionic personality disorder, according to DSM-5 criteria
15. Has met DSM-5 criteria for substance use disorders within the last 6 months prior to Screening, except for disorders related to the use of caffeine or nicotine
16. Has a positive test for an illicit drug at Screening or Baseline. Subjects who test positive for a controlled substance and who have a valid prescription can be enrolled if the drug is not a prohibited medication
17. Actively suicidal at Visit 1 (Screening) or Visit 2 (Baseline) (including an answer of “yes” to Columbia Suicide Severity Rating Scale [C-SSRS] question 4 or 5 [current or over the last 6 months]) or has attempted suicide in the 2 years prior to Visit 1 (Screening)
18. Is pregnant or breastfeeding. Female subjects of child-bearing potential must have a negative serum pregnancy test at Screening [REDACTED]
19. Has major surgery planned during the trial (including Screening and follow-up periods) [REDACTED]
20. Has participated in or is participating in a clinical trial of any investigational drug, device, or intervention, within 60 days (or five half-lives, whichever is longer) prior to Screening [REDACTED]
21. Has previously been treated with pimavanserin or is currently taking pimavanserin
22. Has a sensitivity to pimavanserin or its excipients
23. Is judged by the Investigator or the Medical Monitor to be inappropriate for the study

If a subject is discontinued from the study because of an AE, every reasonable attempt should be made to follow the subject until the AE resolves or until the Investigator deems the AE to be chronic or stable.

All SAEs will continue to be followed until such events have resolved or the Investigator deems them to be chronic or stable.

Should a subject request or decide to withdraw, every reasonable effort will be made to complete and report observations as thoroughly as possible up to the date of withdrawal, including the evaluations specified at the EOT visit outlined in [Table S-1](#). Unless the subject has withdrawn consent to be contacted for this study, every reasonable effort will be made to complete the 2-week safety follow-up telephone call for all subjects who withdraw prematurely. All information will be reported on the applicable pages of the electronic case report form (eCRF).

The Sponsor reserves the right to discontinue the study at any time for any reason. Such reasons may include, but not be limited to, the following:

- Occurrence of AEs unknown to date in respect of their nature, severity, and duration or the unexpected incidence of known AEs
- Medical or ethical reasons affecting the continued performance of the study

Regulatory Authorities also have the right to terminate the conduct of the study in their region for any reason.

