#### **4.5 Prior and Concomitant Therapy**

Lifetime antidepressant use and response is to be recorded. All other medications used within 24 weeks prior to Visit 2 through Visit 7 (telephone visit) or EOT are to be recorded.

In order to ensure that appropriate concomitant therapy is administered, it is [REDACTED] [REDACTED] consultation with the Investigator (unless the subject is receiving treatment for a medical emergency [REDACTED]) [REDACTED] ns

Prohibitions and restrictions for concomitant medications, as specified in [Appendix A](#) and [Appendix B](#), should be followed between Visit 1 (Screening) and Visit 6/EOT. Medications that can prolong QT interval are prohibited (or restricted if approved by the Medical Monitor or appropriate designee) as specified in Appendix A. These appendices do not constitute an exhaustive list and any questions regarding prohibited and restricted medications or the use of medications that could interfere with study conduct should be discussed with the Medical Monitor or appropriate designee.

If a subject is on a restricted or prohibited medication at Screening, the medication should be adjusted or discontinued only if it is determined by the Investigator to be clinically appropriate (e.g., if the subject's symptoms are not well-controlled or if the subject cannot tolerate the current medication).

The Investigator may prescribe, adjust, or discontinue appropriate medication to treat or manage AEs. If a prohibited medication is prescribed to treat an AE, the subject may remain in the study if the Sponsor and Investigator (or designee) determines that it is appropriate for the subject to remain in the study.

All other subjects who take a prohibited medication during the study will be discontinued, unless the discontinuation presents an unacceptable medical risk. The justification to allow a subject to continue in the study will be made by the Sponsor, with medical input from the Investigator, and will be documented. If a subject is allowed to remain in the study on prohibited medication that is not prescribed to treat an AE, this will be reported as a major protocol deviation and not a waiver.

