## 16 APPENDICES

### Appendix A Prohibited and Restricted Medications

Subjects taking prohibited medications at study entry will not be eligible for the study. Subjects taking prohibited medications during the trial will be discontinued, unless the discontinuation presents an unacceptable medical risk. The justification to allow the subject to continue in the trial will be made by the Sponsor/Medical Monitor with medical input from the Investigator, and will be documented. If allowed to remain in the trial, this will be reported as a major protocol deviation and not a waiver.

The table below lists prohibitions and restrictions by medication class, including representative medications within class. Medications within each class include but are not limited to the examples listed in this table. Any questions regarding prohibited and restricted medications should be discussed with the Medical Monitor or appropriate designee.

Medication Class	Medication a	Prohibition/restrictions
Antipsychotics other than pimavanserin	PROHIBITED 
 
All in class
 
	
 
Must be washed out 2 weeks or 5 half-lives (whichever is longer) prior to Baseline
 
All antipsychotics are prohibited
 

Anticholinergics	PROHIBITED 
 
Centrally acting anticholinergics                             
 
benztropine
 
biperiden
 
trihexiphenidyl
 
oral diphenhydramine
 
 
 
	
 
Centrally acting anticholinergic medications are prohibited and should be washed out and discontinued at least 2 weeks or 5 half-lives (whichever is longer) prior to Baseline
 

	UNRESTRICTED 
 
Peripherally acting anticholinergics
 
Topical diphenhydramine
 
	
 
Peripherally acting anticholinergic medications and topical diphenhydramine are allowed without restriction
 

Anticonvulsant and mood stabilizers	PROHIBITED 
 
carbamazepine
 
lamotrigine
 
lithium
 
phenytoin
 
	
 
Must be washed out prior to Baseline or for 5 half-lives of the drug
 
Prohibited throughout the study
 

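### The antipsychotic-free interval before Baseline is 3 weeks or 5 half-lives in Exclusion 1 but 2 weeks or 5 half-lives in Appendix A, so a site that times washout from the appendix can bring an ineligible subject to Baseline.

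*Protocol*

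**What the plan says.** Exclusion 1 has the same wording in the protocol synopsis and in Section 4.3. It excludes a subject for "Use of an antipsychotic within 3 weeks or 5 half-lives of Baseline (whichever is longer").

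Appendix A, in the row for antipsychotics other than pimavanserin, classes the whole group as prohibited and adds: "Must be washed out 2 weeks or 5 half-lives (whichever is longer) prior to Baseline".

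Both provisions bind the sites. Section 4.5 says that the prohibitions and restrictions in the appendices "should be followed between Visit 1 (Screening) and Visit 6/EOT". Section 4.1 says that "subjects must meet all of the inclusion criteria and none of the exclusion criteria", and adds: "Protocol waivers for eligibility will not be granted by the Sponsor under any circumstances". If a subject is found to be ineligible during the study, "she or he will be discontinued, unless the discontinuation presents an unacceptable medical risk"; one who is kept in is reported as a major protocol deviation. Section 10.6 repeats these rules.

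On timing, Section 3.2 says that prohibited medications are discontinued in the screening period and that "Screening will be up to 3 weeks". Table S-1 puts Screening at Day -21 to Day -1 and schedules the inclusion/exclusion assessment at both Screening and Baseline.

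**The concern.** Two current passages give different minimum intervals for the same drug class before the same visit. Each takes the longer of a fixed number of weeks and 5 half-lives, so the 5-half-life term does not remove the difference unless the half-life is long.

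The conflict runs one way: Appendix A is the looser rule. That matters because Appendix A is the natural place for a site to look when it plans a washout. It is organised by drug class, and Section 4.5 points to it. A coordinator who counts the days from Appendix A can book a Baseline visit at which the subject still meets Exclusion 1.

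At stake are consistent eligibility decisions across about 20 sites and avoidable screen failures. If the error is missed at Baseline, the protocol's own text will also have led to a discontinuation or a major deviation. The SAP (Section 7) tabulates major deviations, so their classification reaches the study report.

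**Working it through.** The plan gives no calculated figure for this point, so there is none to reproduce. The check applies both rules to the same subject.

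**Inputs**
- Exclusion 1 (synopsis and Section 4.3): 3 weeks = 21 days, or 5 half-lives, whichever is longer.
- Appendix A: 2 weeks = 14 days, or 5 half-lives, whichever is longer.
- Half-life *h*, in days: the documents give none for any antipsychotic, so it is varied as an assumption.
- *d* = whole days off the antipsychotic at Baseline. Day 21 is taken as satisfying Exclusion 1, although the wording leaves that day open to interpretation.

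**Rules**
- Appendix A is met if *d* ≥ max(14, 5*h*).
- Exclusion 1 is triggered if *d* < max(21, 5*h*).
- The rules conflict if max(14, 5*h*) ≤ *d* < max(21, 5*h*).

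**Where the half-life term takes over**
- Appendix A: 14 / 5 = 2.8 days.
- Exclusion 1: 21 / 5 = 4.2 days.

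| Half-life (days) | 5 half-lives (days) | Appendix A minimum | Exclusion 1 minimum | Days off drug in conflict |
|---|---|---|---|---|
| 1 | 5 | 14 | 21 | 14 to 20 (7 days) |
| 2.8 | 14 | 14 | 21 | 14 to 20 (7 days) |
| 3 | 15 | 15 | 21 | 15 to 20 (6 days) |
| 3.5 | 17.5 | 17.5 | 21 | 18 to 20 (3 days) |
| 4 | 20 | 20 | 21 | 20 only (1 day) |
| 4.2 | 21 | 21 | 21 | none |
| 5 | 25 | 25 | 25 | none |

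The band is therefore a full week for half-lives of up to 2.8 days. It narrows between 2.8 and 4.2 days and is empty from 4.2 days on, where the half-life term governs both rules.

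**Screening window.** The SAP's study-day convention (Section 5.3, note to Table 2) has no Day 0, so Day -21 is 21 days before Day 1. Where the week limits govern, a subject still taking the drug when screening opens must take the last dose by Day -21 to reach 21 days off at Baseline, but only by Day -14 to reach 14 days. The longer interval uses the whole window, and the shorter leaves 21 - 14 = 7 days.

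**Sample size, as a side check.** With SD 6.0, a mean change of 3, a two-sided 0.05 level and 34 evaluable subjects, a paired t-test has power 0.808, against the stated 80%. Then 34 / (1 - 0.15) = 40. Both plan figures reproduce, and neither depends on the washout interval.

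**The case against.** The strongest reply is that the two rules apply together, so the stricter one governs. Section 4.1 requires that no exclusion criterion be met, and Table S-1 repeats the eligibility check at Baseline, before dosing. Meeting Appendix A never makes a subject eligible. This stands: on the text, a subject in the band is excluded at every site. A reader might infer that the protocol sanctions different eligibility decisions at different sites, but the documents do not support that. What remains is a risk of error, because the table that sites are told to follow gives a shorter interval than eligibility requires.

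Three other inferences are tempting and do not hold:

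- **Carry-over into the Baseline scores.** A reader might infer that residual antipsychotic distorts change from Baseline. Both rules require at least 5 half-lives off drug. Assuming first-order elimination, at most (1/2)^5 = 1/32, or about 3%, remains. Nor do the documents state the purpose of the interval.
- **Loss from the non-evaluable allowance.** The plan allows 15% of 40 = 6 non-evaluable subjects, and a reader might count each discontinued subject against those 6. The plan does not define non-evaluable. The Full Analysis Set (Section 9.7.1; SAP 4.2) needs one dose, a Baseline value and one post-Baseline HAMD-17 total, and the MMRM uses observed visits (SAP 13.1.1). A subject discontinued after a post-Baseline rating stays in the primary analysis, and early terminators are asked to complete the Week 8 assessments if possible.
- **A longer interval that cannot be met.** A 3-week washout begun at Screening is tight but not ruled out. Section 4.1 allows some re-screening, though it does not say whether a washout qualifies. A long washout is not peculiar to this rule either: Appendix B sets at least 30 days for CYP3A4 inducers, longer than the screening window.

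It is also fair to say that few subjects are likely to be affected. Exclusion 12 removes those with a history of PD psychosis, other psychotic disorder or bipolar disorder, and Section 3.2 bars stopping a prohibited medication in order to enrol someone. Use as an augmentation agent under Inclusion 7 may remain, but that criterion does not name antipsychotics.

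**Conclusion.** The inconsistency is real and unreconciled: 3 weeks in the synopsis and Section 4.3, 2 weeks in Appendix A, for the same class and the same visit. It opens a band of up to 7 days (days 14 to 20 off drug) in which a subject meets the appendix but is ineligible. The band is full for half-lives of up to 2.8 days and vanishes at 4.2 days.

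The consequence is procedural. A site that times washout from Appendix A can schedule or dose an ineligible subject. The result is a screen failure if it is caught at Baseline. If it is caught later, the subject is discontinued, unless that presents an unacceptable medical risk, in which case the subject may stay in as a major deviation.

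The finding rests on reading both passages as current and binding, which Sections 4.1 and 4.5 support. The documents give no count of affected subjects; the number is probably small. It does not alter the stated sample size or power, and it is no evidence of bias in the primary result. It should be corrected because an eligibility threshold is stated in two ways and the correction is cheap.

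**What to change.** - Reconcile Exclusion 1 in the synopsis, Exclusion 1 in Section 4.3 and the antipsychotic row of Appendix A to a single interval. Which interval is for the sponsor to decide.
- Confirm that the chosen interval is compatible with screening from Day -21 to Day -1, and state how its boundary day is counted.
- Check the antipsychotic stop dates of subjects already enrolled. Where a subject falls between the two limits, apply one classification rule across all sites and record it.

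The cost is a short protocol clarification, with whatever IRB/EC submission Section 10.7 requires, and one data listing. No new data are needed: Section 4.5 already requires other medications used within 24 weeks before Visit 2 to be recorded. The analyses in the SAP do not change.
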